7.5 Duration of Follow Up

Patients will be followed for approximately 180 days after Y90 therapy according to the SoA's detailed above to determine both safety and efficacy. The patients will then be followed every 3 months as per standard of care at Emory IR. This will generally continue until patient's death, enrollment in hospice or loss to follow-up.

Long-term follow-up should continue until the patient's withdrawal of consent or loss to follow up, death, or study termination. In case of a clinically significant AE, patient will be followed for safety until resolution or permanent sequelae of all toxicities attributable to study drug(s). If the patient discontinues study drug for a clinically significant AE, the patient will be followed until resolution of the AE or the event is considered to be stable and/or chronic.

A participant will be considered lost to follow-up if he fails to return for three scheduled visits and is unable to be contacted by the study site staff after three attempts at contact by phone.

The following actions must be taken if a participant fails to return to the clinic for a required study visit:

- The site will attempt to contact the participant and reschedule the missed visit and counsel the participant on the importance of maintaining the assigned visit schedule and ascertain if the participant wishes to and/or should continue in the study.
- Before a participant is deemed lost to follow-up, the investigator or designee will make every effort to regain contact with the participant (where possible, 3 telephone calls and, if necessary, a certified letter to the participant's last known mailing address or local equivalent methods). These contact attempts should be documented in the participant's medical record or study file.
- Should the participant continue to be unreachable, he will be considered to have withdrawn from the study with a primary reason of lost to follow-up.

7.6 Discontinuation of Study Intervention

Discontinuation from low-dose Y90 mapping study does not mean discontinuation from the study, and remaining study procedures should be completed as indicated by the study protocol. If a clinically significant finding is identified (including, but not limited to changes from baseline) after enrollment, the investigator or qualified designee will determine if any change in participant management is needed. Any new clinically relevant finding will be reported as an adverse event (AE).

Patients may choose to discontinue the trial at any time, for any reason, and without prejudice to further treatment. The EOT visit will occur 30 days after the last dose of the radiopharmaceutical administration.

Reasons for EOT are:

- PD in the absence of clinical benefit as determined by the Investigator.
- Occurrence of a clinically significant AE found to be unacceptable or non-resolution of clinically significant AEs for > 6 weeks.
- Symptomatic deterioration.
- Achievement of maximal response.
- Noncompliance of the patient with protocol-mandated procedures based on the judgment and agreement of both the Investigator and Sponsor.
- Continued participation is no longer in the patient's best interest in the opinion of the Investigator.
- Withdrawal of consent.

Patient remain on treatment phase until discontinuation of all study drugs, In the event of a patient's withdrawal, the Investigator will promptly notify the Sponsor and make every effort to complete the EOT procedures specified in the Schedule of Events. The reason for participant discontinuation or withdrawal from the study will be recorded on the Case Report Form (CRF). Subjects who sign the informed consent form and are assigned but do not receive the study intervention may be replaced. Subjects who sign the informed consent form, and are assigned and receive the study intervention, and subsequently withdraw, or are withdrawn or discontinued from the study, will not be replaced.

The data to be collected at the time of study intervention discontinuation will include the following: the reason for discontinuation and any imaging and laboratory follow-up.

7.7 Withdrawal from the Study

Participants are free to withdraw from participation in the study at any time upon request. An investigator may discontinue or withdraw a participant from the study for the following reasons:

- Pregnancy
- Significant study intervention non-compliance
- If any clinical adverse event (AE), laboratory abnormality, or other medical condition or situation occurs such that continued participation in the study would not be in the best interest of the participant
- Disease progression which requires discontinuation of the study intervention
- If the participant meets an exclusion criterion (either newly developed or not previously recognized) that precludes further study participation
- Participant unable to receive Y90 therapy

The reason for participant discontinuation or withdrawal from the study will be recorded on the Case Report Form (CRF). Subjects who sign the informed consent form and are randomized but do not receive the study intervention may be replaced. Subjects who sign the informed consent form and subsequently withdraw, or are withdrawn or discontinued from the study will be replaced.

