5. STUDY POPULATION

5.1 Inclusion Criteria

Study candidates must meet all of the following inclusion criteria to be eligible for participation in this study:

- a. Adults \geq 18 years
- b. Life expectancy of 6 months or more as determined by the investigator
- c. HCC confirmed by Liver Reporting & Data System (LIRADS) on MRI or CT
- d. Must have measurable disease, defined as at least one lesion that can be accurately measured in at least one dimension (longest diameter to be recorded for non-nodal lesions and short axis for nodal lesions) as \geq 20 mm (\geq 2 cm) with CT scan, MRI, or calipers by clinical exam. See Section 12 (Measurement of Effect) for the evaluation of measurable disease.
- e. \leq 3 lesions
- f. Longest dimension of the largest lesion \leq 7cm
- g. Single lobe disease
- h. No significant extrahepatic metastatic disease
- i. Barcelona Clinic Liver Cancer Stage A, B or C
- j. ECOG $<$ 2 (Appendix A)
- k. Lesion(s) $<$ 50% of liver volume
- l. Bilirubin \leq 2 mg/dL
- m. Albumin \geq 3 g/dL
- n. PT/INR $<$ 2
- o. AST/ALT \leq 3 institutional upper limit of normal (ULN)
- p. Platelet count $>$ 50,000/mcL
- q. Lung shunt fraction of $<$ 20% by planar MAA if dose modification results in inadequate dose delivered to the tumor(s)
- r. Patients with a prior or concurrent malignancy whose natural history or treatment does not have the potential to interfere with the safety or efficacy assessment of the investigational regimen are eligible for this trial.
- s. Completion of all previous therapy (including surgery, radiotherapy, chemotherapy, immunotherapy, or investigational therapy) for the treatment of cancer \geq 12 week before the start of study therapy.
- t. Willingness and ability of the subject to comply with scheduled visits, drug administration plan, protocol-specified laboratory tests, other study procedures, and study restrictions.
- u. Evidence of a personally signed informed consent indicating that the subject is aware of the neoplastic nature of the disease and has been informed of the procedures to be followed, the experimental nature of the therapy, alternatives, potential risks and discomforts, potential benefits, and other pertinent aspects of study participation.
- v. The effects of *Y90 microspheres* on the developing human fetus are unknown. For this reason female of child-bearing potential (FCBP) must have a negative serum or urine pregnancy test prior to starting therapy.

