5.2 Exclusion Criteria

An individual who does not meet all the inclusion criteria in section 5.1.

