Assessments for subjects who have completed treatment and achieved disease control, or have discontinued treatment due to toxicity in the absence of confirmed progressive disease are provided in the Schedule of Event.

All subjects will be followed for survival until the end of the study regardless of further treatments, or until the sponsor ends the study.

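### Section 7.7 allows treated patients to be withdrawn from the study for toxicity or a newly failed entry limit, in conflict with the follow-up in 7.5, so late safety and response data can be lost selectively

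*Combined protocol and SAP*

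**What the plan says.** Section 7.7 (Withdrawal from the Study) lists grounds on which an investigator may remove a participant from the study itself, not only from the intervention. Three matter here:

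- Newly met exclusion: "If the participant meets an exclusion criterion (either newly developed or not previously recognized) that precludes further study participation".
- Toxicity or laboratory change: "If any clinical adverse event (AE), laboratory abnormality, or other medical condition or situation occurs such that continued participation in the study". The rest of that clause makes this a judgement about the participant's interest.
- Progression: "Disease progression which requires discontinuation of the study intervention".

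None is limited to the time before therapeutic Y90. Section 5.2 contains one exclusion criterion: "An individual who does not meet all the inclusion criteria in section 5.1". Section 5.1 sets limits on bilirubin, albumin, PT/INR, AST/ALT, platelets, ECOG, lesion number and size, and extrahepatic disease, and requires "Single lobe disease".

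Section 7.5 follows patients for about 180 days after Y90 according to the Schedule of Activities. It ends long-term follow-up at withdrawal of consent, loss to follow-up, death or study termination. Section 8.1 adds: "All subjects will be followed for survival until the end of the study regardless of further treatments, or until the sponsor ends the study".

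**The concern.** Read together, 5.2 and 7.7 turn entry limits into possible reasons for leaving the study after treatment. Several of those limits are also what the 1-, 3- and 6-month visits measure: blood counts, the metabolic panel, ECOG, and the number and location of lesions. Missingness may then depend on toxicity.

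Safety is part of the primary objective (section 3). Response and the tumor dose response threshold (TDRT) are secondary. If the patients who tolerate treatment worst are the ones whose later tests and scans are missing, the 3- and 6-month results describe a healthier subset. With 30 patients, a few such losses are visible in the rates.

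**Working it through.** The plan gives no withdrawal, toxicity or response rate, so it has no figure to reproduce on this point. The check compares sections, then uses arithmetic on assumed counts.

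**Step 1. Which limits can newly fail and be seen at follow-up?** The 8.1 follow-up visits list hematology, metabolic panel, ECOG and liver CT or MRI. These cover platelets, bilirubin, albumin, AST/ALT, ECOG and liver disease extent. INR is not routine after baseline: 8.2 has it at baseline and as clinically indicated.

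**Step 2. What follow-up remains after an investigator withdrawal?**

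- 7.5 does not list investigator withdrawal as an end of long-term follow-up, whereas 7.7 ends study participation. No section says which prevails or states that scheduled tests and scans continue.
- 8.1 conflicts with 7.7 for survival only.
- Adverse events are partly protected. 7.3.3 runs to 150 days after discontinuation or to new antineoplastic medication, whichever is sooner, and collects suspected SAEs beyond that. 7.5 follows clinically significant events to resolution. 11.5.1 and 11.5.2 give 90-day windows after treatment ends.
- 10.5 instead counts from the last day of study participation: 7 days for non-serious and 100 days for serious events. On that clock, withdrawal at month 1 closes non-serious capture a week later. 11.5.1 notes that a grade 3 or 4 event is not automatically serious.
- For a single session, the 90- and 150-day windows end before the 6-month visit (180 − 90 = 90 and 180 − 150 = 30 days short).

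**Step 3. How are the resulting gaps analysed?**

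- Response: 10.5.3 uses the 90- and 180-day assessments. Patients unassessed because of early progression or death count as non-responders. Those unassessed for other reasons leave the denominator, and a toxicity, laboratory or ECOG withdrawal falls there.
- PFS: 10.5.4 censors patients without an event at the last clinical assessment. That is informative if toxicity is related to later progression or death.
- Replacement: 7.7 replaces withdrawn subjects and 10.2 recruits a new patient after a dropout. 7.6 says those who received the intervention are not replaced.

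**Step 4. Illustration for response (all counts assumed).** R responders among 30 treated; w patients withdrawn for toxicity, none of whom would have responded. True rate = R/30; reported rate = R/(30 − w). Exact 95% intervals in brackets.

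| R | w = 0 | w = 3 | w = 6 |
|---|---|---|---|
| 9 | 30.0% (14.7–49.4) | 33.3% (16.5–54.0) | 37.5% (18.8–59.4) |
| 12 | 40.0% (22.7–59.4) | 44.4% (25.5–64.7) | 50.0% (29.1–70.9) |
| 15 | 50.0% (31.3–68.7) | 55.6% (35.3–74.5) | 62.5% (40.6–81.2) |

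The upward shift is 3.3 to 5.6 points for w = 3 and 7.5 to 12.5 points for w = 6.

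**Step 5. Illustration for toxicity (assumed).** Suppose 4 of 30 patients have a grade 3 or higher liver event, and 2 of these would be found only at later visits that a withdrawn patient no longer attends. Then 4/30 = 13.3% is reported as 2/30 = 6.7%. This requires that none of the safeguards in step 2 catches the two events.

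**The case against.** The strongest reply is that 7.7 is discretionary and every ground is qualified. The investigator may withdraw; the newly met criterion must preclude further participation; the laboratory ground turns on best interest. A bilirubin above 2 mg/dL at month 1 does not by itself prevent a follow-up visit. The eligibility ground also has a proper use, because 7.4.1 provides for a second session if eligibility is maintained. Section 8.1 refers patients who stopped for toxicity to the Schedule, and 7.6 asks for imaging and laboratory follow-up at discontinuation.

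Most of this stands, and it rules out several stronger readings that a reader might infer:

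- That crossing an entry limit forces withdrawal: the text only permits it.
- That progression removes patients from the results: that ground needs an intervention left to stop, which is rare after a single session. Documented progression is already a PFS event, and 10.5.3 keeps early progression in the denominator.
- That safety capture ends at withdrawal: 7.3.3, 7.5 and 11.5 continue much of it.
- That 8.1 promises scans and laboratory tests to everyone: the sentence quoted above covers survival only.
- That the MAA versus low-dose Y90 comparison is biased: both mapping studies precede therapy.

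The reply does not remove the gap. Discretionary withdrawal linked to outcome is harder to correct in analysis than a fixed rule, and no sentence keeps an investigator-withdrawn patient in scheduled data collection.

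**Conclusion.** The concern holds in a limited form. Section 7.7 permits withdrawal of treated patients for toxicity, laboratory change or a newly failed entry limit, and it is not reconciled with 7.5 or, for survival, with 8.1. The exposed results are late laboratory toxicity, 3- and 6-month response, TDRT and PFS. The main route is withdrawal for toxicity, laboratory values or ECOG.

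The size cannot be estimated from the documents. Under the assumed counts, the response rate rises by 3 to 13 percentage points. This assumes 3 to 6 such withdrawals among 30 and no responders among those lost. The toxicity illustration (13% read as 7%) is less secure, because the other adverse-event rules may catch some or all of those events. The point should be corrected, but it does not threaten the LSF and TNR comparison.

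**What to change.** In 7.7, separate two decisions:

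- **Stopping study intervention or procedures.** Keep every listed ground, including pregnancy, best interest and eligibility for a second session, at the investigator's discretion.
- **Ending data collection.** State that after therapeutic Y90 it ends only at withdrawal of consent, death, loss to follow-up or study termination. Laboratory, imaging and survival data obtained in standard-of-care follow-up at 1, 3 and 6 months continue to be collected.

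In section 10, state that all treated patients stay in the safety and response analyses, and that those unassessed because of a toxicity withdrawal count as non-responders. Reconcile 7.7 with 7.5 and 8.1, and the replacement rules in 7.6, 7.7 and 10.2.

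The cost is protocol wording and slightly more data collection, since 4.1 describes the follow-up visits as standard of care. The response rate may look less favourable.

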4.3 Justification for Dose

Based on our phantom study to minimize scatter on SPECT/CT and to ensure adequate activity to be imaged using PET, 15 mCi of low-dose Y90 is found to be adequate. Additionally, in a hypothetical patient with a LSF of 100% (usually ~10% in HCC patients), 15 mCi of Y90 activity will result in 27.8 Gy of radiation to the lungs which is within the accepted limits of 30 Gy per treatment session. Such patient will not be a candidate a for therapeutic Y90 dose so cumulative dose to the lungs will remain below 30 Gy.

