10.5 Safety Analyses

Adverse event data will be described and graded per the NCI CTCAE 5.0 guidelines. For each adverse event, information to be collected includes event description, time of onset, clinician assessment of severity, relationship to study product (assessed only by those with the training and

authority to make a diagnosis), and time of resolution/stabilization of the event. Regardless of relationship, all AEs will be recorded with start dates occurring any time after patient receives Y90 until 7 (for non-serious AEs) or 100 days (for SAEs) after the last day of study participation. At each study visit, the investigator will inquire about the occurrence of AE/SAEs since the last visit. Events will be followed for outcome information until resolution or stabilization.

Any medical condition that is present at the time that the participant is screened will be considered as baseline and not reported as an AE. However, if the study participant's condition deteriorates at any time during the study, it will be recorded as an AE. Changes in the severity of an AE will be documented to allow an assessment of the duration of the event at each level of severity to be performed. AEs characterized as intermittent require documentation of onset and duration of each episode.

The maximum grade for each type of toxicity will be recorded for each patient, and frequency tables will be reviewed to determine toxicity patterns. Adverse events will be summarized and described within each cohort. They will initially be reviewed regardless of attribution, but also whether they are possibly, probably, or definitely related to treatment. In addition, we will review all adverse event data that are graded as 3, 4, or 5 and classified as either "unrelated" or "unlikely to be related" to study treatment in the event of an actual relationship developing. The incidence of severe adverse events or toxicities will be described. We will assess the proportion of patients who experience grade 3 or higher non-hematologic toxicity. To assess tolerability, we will also capture the proportion of patients who go off treatment due to adverse events.

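### Patients given low-dose Y90 but no therapy are not reliably followed or counted for safety, yet only in them is later toxicity of the 15 mCi unconfounded by study therapy

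*Combined protocol and SAP*

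**What the plan says.** Section 3 places safety in the primary objective, and section 4.1 identifies the second mapping procedure with 15 mCi of Y90 as the added intervention. Sections 1.3 and 8.1 put MAA and low-dose Y90 on Monday, dosimetry on Tuesday/Wednesday and therapy on Wednesday/Thursday. Section 4.3 considers a patient with extreme lung shunting who has had the low dose: "Such patient will not be a candidate a for therapeutic Y90 dose so cumulative dose to the lungs will remain below 30 Gy".

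Section 7.7 then provides: "An investigator may discontinue or withdraw a participant from the study for the following reasons". One of the reasons is "Participant unable to receive Y90 therapy". Section 7.5 states: "Patients will be followed for approximately 180 days after Y90 therapy according to the SoA's detailed above". Section 8.1 dates the phone call from therapy, and sections 8 and 9.1 date follow-up imaging and response from therapy. The Schedule of Activities heads its follow-up columns as post-procedure without naming the procedure. Section 9.1 makes patients evaluable for toxicity from their first treatment with Y90 therapy.

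Other passages still reach this patient:

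- **Section 7.6:** "The EOT visit will occur 30 days after the last dose of the radiopharmaceutical administration". It also asks for every effort to complete the end-of-treatment procedures on withdrawal.
- **Section 10.5:** adverse events are recorded once the patient receives Y90, "until 7 (for non-serious AEs) or 100 days (for SAEs) after the last day of study participation".
- **Section 11.5.1:** recording runs to 90 days after treatment ceases.
- **Section 7.3.3:** adverse-event follow-up runs to 150 days after discontinuation or to new antineoplastic medication, whichever is sooner.

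On replacement, section 7.7 says "Subjects who sign the informed consent form and subsequently withdraw, or are withdrawn or discontinued from the study will be replaced" and section 10.2 agrees. Section 7.6 says that those who received the intervention "and subsequently withdraw, or are withdrawn or discontinued from the study, will not be replaced".

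**The concern.** In a treated patient, therapeutic Y90 follows the low dose by two or three days. A lung or liver event appearing weeks later cannot be assigned to one or the other. In a patient who has the low dose alone, a late event is at least not confounded by study therapy. These few patients are therefore the most direct evidence on the later toxicity of the added intervention, and the plan's own dose justification relies on one of them as its limiting case.

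They are also the patients whom the follow-up rules fit worst. With no therapy date, the main visits have no starting point. With withdrawal allowed, participation can end within days of exposure. With toxicity evaluability tied to therapy, even events that are recorded may be left out of the tables. If such patients are also replaced, the final 30 could consist only of treated patients. A report of no low-dose toxicity would then partly reflect who was observed.

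**Working it through.** **1. Exposure.** Formula 6 in section 7.1.2 gives lung dose = activity (GBq) × LSF × 50 / lung mass, with lung mass taken as 1 kg. Activity is 15 mCi × 0.037 = 0.555 GBq.

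- LSF 100%: 0.555 × 1.00 × 50 = 27.75 Gy. This reproduces the 27.8 Gy in section 4.3.
- LSF 50%: 13.9 Gy
- LSF 30%: 8.3 Gy
- LSF 20%: 5.6 Gy
- LSF 10%, the level section 4.3 calls usual: 2.8 Gy

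All lie below the 30 Gy limit in section 4.3. The exposure is real but within what the plan accepts, so the question is whether it is observed.

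**2. How long adverse events are collected.** Let day 0 be the Monday low dose. Assume that withdrawal, if it happens, is on Thursday (day 3), that the Monday dose counts as treatment, and that no new anticancer therapy starts.

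| Rule | Non-serious AEs end | SAEs end |
|---|---|---|
| 10.5, participation ends at withdrawal | 3 + 7 = day 10 | 3 + 100 = day 103 |
| 10.5, participation ends at the 30-day visit of 7.6 | 30 + 7 = day 37 | 30 + 100 = day 130 |
| 11.5.1 and 11.5.2, 90 days after treatment ceases | day 90 | day 90 |
| 7.3.3, 150 days after discontinuation | day 150 | day 150, suspected SAEs beyond |
| For comparison, 10.5 in a patient treated on day 3 and followed 180 days | 3 + 180 + 7 = day 190 | 3 + 180 + 100 = day 283 |

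For one and the same low-dose-only patient, the end of non-serious collection ranges from day 10 to day 150.

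**3. The end-of-treatment visit.** Section 7.6 sets it 30 days after the last radiopharmaceutical dose. Section 8.1 says that, for early discontinuation, end of treatment is the visit at which the decision is made, with procedures within 7 days either way. For a patient found unsuitable on Wednesday, the second rule puts it within days of exposure. Section 8.2 assigns a full physical examination at this visit, but the Schedule of Activities has no column for it and so assigns it no blood tests.

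**4. Who is counted.** Section 10.5 starts recording when the patient receives Y90, which takes in the low dose. Section 9.1 starts toxicity evaluability at Y90 therapy, which does not. Read literally, a low-dose-only patient's events are recorded but fall outside the evaluable set.

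**5. How many.** The documents give no non-treatment rate. If a share f is not treated and recruitment continues until 30 are, the number exposed is 30/(1 − f), rounded up:

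- f = 5%: 32 exposed, 2 low-dose only
- f = 10%: 34 exposed, 4 low-dose only
- f = 20%: 38 exposed, 8 low-dose only

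With zero events in k patients, the one-sided 95% upper bound is 1 − 0.05^(1/k): 63% for k = 3 and 39% for k = 6. Full capture would describe these patients without estimating a rate with any precision.

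**The case against.** The best case for the plan is section 7.3.3. It requires adverse-event follow-up of all patients for up to 150 days by clinic visits, laboratory checks and calls, and does not tie this to therapy. Section 7.5 adds follow-up of clinically significant events to resolution, section 7.6 has its 30-day visit, and section 8.1 follows everyone for survival. Withdrawal under 7.7 is permitted, not required.

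This stands against several stronger readings that a reader might infer:

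- **That these patients are lost altogether, or that all follow-up runs from therapy.** The passages just listed rule this out.
- **That non-serious events are collected for about one week instead of six months.** Day 10 is only the shortest of several conflicting answers.
- **That high shunting is a main reason for non-treatment.** The documents give no such breakdown. MAA imaging precedes the low dose on the same day, so a high MAA shunt can be known beforehand, although no check is written in between. At LSF of 20% or more, section 7.1.3 modifies the dose and does not refuse treatment outright.
- **That these are the only patients who can show low-dose toxicity.** Every patient has a two- to three-day interval before therapy in which acute complications of the second angiography could appear. No blood tests are scheduled after the low dose until the 1-month visit, so that interval says little about delayed lung or liver effects.

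The objection does not close the gap. No visit in the Schedule of Activities carries out section 7.3.3 for a patient without a therapy date. Section 11.5.1 records events at examinations, and those scheduled after mapping are timed from therapy. Following an event to resolution presupposes that it was detected. None of these passages overrides the evaluability rule in section 9.1.

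**Conclusion.** The point holds as a matter of unreliable follow-up and counting. Three stated rules (optional withdrawal in 7.7, follow-up dated from therapy in 7.5 and 8.1, evaluability from therapy in 9.1) can together leave low-dose-only patients out of the primary safety result. The passages that would keep them in disagree on the end-of-treatment visit, the adverse-event window and replacement.

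The size is small in numbers: perhaps 1 to 3 of 30, an assumption with no figure in the documents behind it. The gain is descriptive and does not bear on power or on the LSF and TNR comparisons. It is worth making because safety is in the primary objective and the change is cheap.

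**What to change.** - **Sections 9.1 and 10.5:** define the safety population as all patients given any Y90, whether low-dose or therapeutic.
- **Section 7.7:** state that being unable to receive therapy does not end safety follow-up.
- **Section 7.5 and the Schedule of Activities:** for patients not treated, time the 1-week call and the 1, 3 and 6 month visits and blood tests from the last Y90 administration of any activity. Add an end-of-treatment column with its procedures.
- **Reconcile** the end-of-treatment timing (7.6 against 8.1), the adverse-event windows (7.3.3, 10.5, 11.5.1, 11.5.2) and the replacement rule (7.6 against 7.7 and 10.2). If such patients are replaced, say that they still stay in the safety population.
- **Section 10.5:** report low-dose-only patients separately, with the date of any later anticancer therapy.

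No dose or treatment decision changes. The cost is a short amendment and a few extra visits and blood tests. The drawback is that later therapies may confuse the attribution of late events, which is why their dates need to be recorded.
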